10.6 Grading the severity of the AE

The NCI CTCAE v4.0 must be used to determine the grade of the AE. The CTCAE provides descriptive terminology and a grading scale for each AE listed. Information regarding the CTCAE can be found on the CTEP Web site at <http://ctep.cancer.gov>. If you need further assistance, contact DSSM (see [Information Resources](#)).

10.7 Expedited reporting instructions

10.7.1 *Time period for reporting SAEs and other events requiring expedited reporting*

- All SAEs and other events as noted in [Sections 10.3](#) and [10.4](#) regardless of relationship to study therapy will be reported in an expedited manner as described in [Section 10.7](#). Reporting SAEs (and other applicable events) regardless of relationship to study therapy begins with the first dose of study therapy and continues until 90 days after the last dose of study therapy.
- Any SAE assessed as related to study participation (e.g., protocol-mandated procedures) will be recorded from the time a patient consents to participate in the study up to and including any follow-up contact.
- Following the AE assessment 90 days after the last dose of study therapy, only SAEs determined to be related to study therapy will be reported in an expedited manner using FC-9 Form SAER.
- The investigator must follow up on all SAEs until the events have subsided, until values have returned to baseline, or until the condition has stabilized.

10.7.2 *Reporting instructions*

- All SAEs and other events requiring expedited reporting (e.g., AESIs \geq Grade 2) must be reported using FC-9 Form SAER (eCRF) and submitted to DSSM within 24 hours of the study site personnel's initial notification of the event.
- When reporting potential Hy's Law cases, Form SAER should include the following:
 - Seriousness Criteria = Important Medical Event
 - Assessments and narrative: Include the term “Potential Hy’s Law case” in the narrative; the text should also detail what additional study results are available at the time of reporting and what other studies are planned or results pending to further investigate alternative causes of the abnormal ALT/AST or bilirubin that triggered the report. The timing of planned patient follow-up should also be noted.
- NSABP will forward expedited report forms that meet reporting requirements to the FDA and to Astra Zeneca/MedImmune Pharmacovigilance.
- Investigators are responsible for reporting AEs that meet specific criteria to their local IRBs.

10.8 Time period and frequency for routine reporting of AEs

- Patients will be monitored for the occurrence of AEs at each scheduled assessment and during any contact with the patient during the study.
- All AEs, including SAEs and other AEs that have been reported on FC-9 Form SAER, regardless of relationship to study therapy, will be recorded on Form AE of the CRF from the first dose of study therapy until 90 days after the last dose of study therapy.

- If the patient stops study therapy and begins a new treatment, AE assessments should be collected *only* up to the date the new therapy begins.
- For routine reporting, **all \geq Grade 1 AEs** will be reported on Form AE of the CRF.
- The investigator must follow up on all AEs until the events have subsided, until values have returned to baseline, or until the condition has stabilized.
- Following the AE assessment 90 days after the last dose of study therapy, routine reporting is no longer required. (See [Section 10.4](#) for expedited reporting requirements.)

10.9 **Documentation requested following death**

For deaths that occur within 30 days of the last dose of study therapy:

- Autopsy reports should be secured whenever possible and should be submitted to DSSM.
- A copy of the death certificate should be forwarded to DSSM if it is readily available or if it contains important cause-of-death information that is not documented elsewhere.
- Submit the last clinic/office note made before the death or the investigator's note summarizing events resulting in death.

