In another model, Sharabi et al. reported that stereotactic radiation induces endogenous antigen-specific immune responses when it is combined with PD-1 checkpoint blockade ([Sharabi 2015a](#)). Using a small animal radiation research platform (SARRP), image-guided stereotactic radiation was delivered to B16-OVA melanoma or 4T1-HA breast carcinoma tumors resulting in the development of antigen-specific T cell- and B cell-mediated immune responses. These immune-stimulating effects of stereotactic radiation were significantly increased in combination with PD-1 pathway blockade, resulting in improved local tumor control. Stereotactic radiation is reported to have several effects on the immune system including increasing the percentage of antigen-experienced T cells and effector memory T cells, upregulating tumor-associated antigen-MHC complexes, enhancing antigen cross-presentation in the draining lymph node, and increasing T-cell infiltration into tumors.

2.7.3 ***The optimal dose and schedule of radiation when combined with immune checkpoint inhibitors***

The optimal fractionation regimen for augmenting immunogenicity of tumors and inducing immune response in patients is unknown ([Demaria 2012](#)). In this study, three daily doses of palliative SBRT at 9 Gy per day in a total of 27 Gy will be administered three days (Days -2, -1, and Day 0) prior to the initial administration of study therapy (durvalumab/tremelimumab). The choice of dose and schedule is based on observations by Twyman-Saint Victor et al. ([Twyman-Saint Victor 2015](#)) and Sharabi et al. ([Sharabi 2015b](#)), that hypofractionated radiation at a dose of 5–20 Gy per fraction is considered to be better than conventionally fractionated schedule of 1.8–2.2 Gy fractions and that concurrent checkpoint blockade starting on the day of or during radiation was better than starting checkpoint blockade after the completion of radiation ([Sharabi 2015b](#)).

2.8 **Rationale for the combination of radiation and dual checkpoint blockade**

Twyman-Saint Victor et al. reproduced the synergistic effect of radiation and anti-CTLA4 therapy in mouse models to further characterize the mechanism ([Twyman-Saint Victor 2015](#)). Although combined treatment improved responses in irradiated and unirradiated tumors, resistance to the combination therapy was common. Analyses of these mouse models revealed that resistance to the combination of radiation and anti-CTLA4 treatment was due to upregulation

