Aim: To determine the safety of the combination of dual immune checkpoint blockade with durvalumab plus tremelimumab following hypofractionated palliative radiation in patients with MSS mCRC who have progressed on chemotherapy.

Endpoint: Frequency and severity of adverse events categorized using the NCI Common Terminology Criteria for Adverse Events version 4.0 (CTCAE v4.0).

3.3 **Exploratory Translational Science**

Aim: To explore the effect of the combination of dual immune checkpoint blockade with durvalumab plus tremelimumab following hypofractionated palliative radiation on immune response in blood and in tumor tissue.

Aim: To correlate the frequency of mutation-associated neoantigens in tumor tissues and clinical response.

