- 4.2.19 Known history or confirmation of active pneumonia, pneumonitis, symptomatic interstitial lung disease, or definitive evidence of interstitial lung disease described on CT scan, MRI, or chest x-ray in asymptomatic patients; dyspnea at rest requiring current continuous oxygen therapy.
- 4.2.20 Active or prior documented autoimmune disease or inflammatory condition requiring ongoing immunosuppressive medications. (Note: Patients with vitiligo, Grave disease, or psoriasis not requiring systemic treatment within the past 2 years are eligible.)
- 4.2.21 Other malignancies unless the patient is considered to be disease-free and has completed therapy for the malignancy \geq 12 months prior to study entry. Patients with the following cancers are eligible if diagnosed and treated within the past 12 months: carcinoma in situ of the cervix, and basal cell and squamous cell carcinoma of the skin.
- 4.2.22 Psychiatric or addictive disorders or other conditions that, in the opinion of the investigator, would preclude the patient from meeting the study requirements or interfere with interpretation of study results.
- 4.2.23 Pregnancy or lactation at the time of study entry. (Note: Pregnancy testing should be performed within 14 days prior to study entry according to institutional standards for women of childbearing potential.)
- 4.2.24 Use and/or receipt of the last dose of anti-cancer therapy (i.e., chemotherapy, immunotherapy, endocrine therapy, targeted therapy, biologic therapy, tumor embolization, monoclonal anti-bodies) within 14 days prior to the first dose of study therapy. (Note: SBRT is required prior to beginning study therapy.)
- 4.2.25 Use of any investigational agent within 4 weeks of starting study therapy.

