8.0 TREATMENT MANAGEMENT

8.1 General instructions

- The NCI CTCAE v4.0 must be used to grade the severity of AEs.
- All treatment decision must be based on the AE requiring the greatest modification.
- Drug doses that have been reduced may not be re-escalated.
- All hematologic, gastrointestinal, and genitourinary toxicities must be < Grade 2 prior to initiating Dose 1 of study therapy. Patients unable to receive Dose 1 will be considered screen failures.

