3.3.2 Safety Population

The Safety population will consist of all patients who receive at least one dose of any study medication.

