3.4 Calculated Variables

- Study day 1 is defined as the first day any of the study therapy was received.
- The baseline is defined as the last assessment done before or on study day 1.
- Duration of Response (months): (earliest date of censoring, progression, or death – earliest date of response + 1) * 365.25 / 12.
- The cycle start date is the first date of administration of any study drug (with a non-missing dose) by treatment cycle (as reported in the eCRF).
- The visit of premature discontinuation of each drug will be derived from [the date of the last dose reported on the form of discontinuation. This date will be merged with the date of drug administration to determine to which cycle of treatment it corresponds.

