6.2 Adverse Events

Frequency and severity of adverse events categorized using the NCI Common Terminology Criteria for Adverse Events version [4.0 (CTCAE v4.0)] will be tabulated. The adverse events are coded using MedDRA Version [18.1]. AE rates will be described by dose level without regard to attribution. Treatment Emergent Adverse events (TEAEs) will be analyzed in terms of their type, incidence and severity. An adverse event is treatment emergent if it occurs on or after the date of the first administration of study drug. According to the protocol, only treatment emergent AEs are collected on this study.

A summary table including the number of AEs and the number of patients with at least one:

- AE
- Grade 1/2 AE
- Grade 3 or 4 AE
- Serious AE
- AE leading to permanent discontinuation of either one of both study treatments
- Fatal AE
- AE leading to death

will be presented.

Tabulations of the number of patients who experienced treatment emergent adverse events as well as grade of the events will be presented by system organ class and preferred term. Patients will only be counted once for each preferred term. In case a patient experienced the same event more than once, the worst grade will be presented.

Listings of all AEs detailing all AE information by patient with flags for SAE, AE leading to treatment discontinuation, Fatal AE, and AE leading to death.

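### Routine AE recording and the SAP safety definitions start at the first drug dose, which leaves a gap for the SBRT days and for irradiated patients who are never dosed

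*Combined protocol and SAP*

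**What the plan says.** **Safety aim.** Protocol 3.2.3: "To determine the safety of the combination of dual immune checkpoint blockade with durvalumab plus tremelimumab following hypofractionated palliative radiation".

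**Order of treatment.** Protocol 7.0 and 14.1 put three SBRT fractions of 9 Gy on Days -2, -1 and 0, and the drugs on Cycle 1 Day 1. Ineligibility item 4.2.24 notes that "SBRT is required prior to beginning study therapy". Section 2.7.3 places the radiation "prior to the initial administration of study therapy (durvalumab/tremelimumab". In these documents, study therapy is therefore the two drugs, and SBRT precedes it.

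**Recording window.** Under 10.8, AEs "will be recorded on Form AE of the CRF from the first dose of study therapy until 90 days after the last dose". Under 10.7.1, expedited SAE reporting irrespective of causality opens at the same point. SAEs judged related to taking part in the study, with protocol-mandated procedures as the example, are recorded from consent.

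**Patients not dosed.** Section 8.1 requires hematologic, gastrointestinal and genitourinary toxicity below Grade 2 before Dose 1, and adds: "Patients unable to receive Dose 1 will be considered screen failures".

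**SAP.** The Safety population (3.3.2) is "all patients who receive at least one dose of any study medication". Section 6.2 states: "An adverse event is treatment emergent if it occurs on or after the date of the first administration of study drug". It then says that, under the protocol, no other AEs are collected.

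**The concern.** The regimen under study is radiation followed by two checkpoint inhibitors, and the radiation is given because the protocol requires it. Protocol 10.1 counts any untoward event in a participating patient as an AE whatever its cause, and gives events from required procedures as an example. Section 8.6.1 expects that SBRT may worsen the toxicity of the drugs, and that some events may have to be attributed to the combination. Yet the clock for routine recording starts only after 27 Gy has been delivered.

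Two things are at stake. An acute event on the SBRT days may never reach Form AE. And a patient who is irradiated but then cannot be dosed leaves the safety denominator. That second loss can depend on toxicity, because toxicity is one of the reasons for withholding Dose 1. The patient is then removed because of the kind of outcome that the safety tables are meant to count.

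**Working it through.** **Step 1: the plan's own figures.** The only computed design figures are those of the Simon design in protocol 14.2 (12 then 21 evaluable patients; stop at 0 responses; reject at 2 or fewer).
- Early termination at ORR 0.05: 0.95^12 = 0.5404 (stated 0.54).
- Expected sample size: 12 + (1 - 0.5404) x 9 = 16.14 (stated 16.14).
- Probability of passing: sum over x = 1 to 12 of P(Bin(12, p) = x) x P(Bin(9, p) >= 3 - x). At p = 0.05 this is 0.0804 (stated 0.080). At p = 0.20 it is 0.8033, so beta = 0.1967 (stated 0.197).

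All reproduce. None depends on the AE window, so the fix leaves them unchanged.

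**Step 2: what is recorded, by type and onset.**

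| Event | Recording required? | Within the SAP definitions? |
|---|---|---|
| Non-serious, first fraction to Dose 1 | No (10.8) | No |
| SAE in that interval, not judged related to participation | No (10.7.1) | No |
| SAE in that interval, related to participation | Yes, from consent (10.7.1) | Not treatment-emergent (SAP 6.2) |
| Any event after Dose 1, including delayed radiation toxicity | Yes, whatever the attribution (10.8) | Yes |
| Any event in an irradiated patient never dosed | Only SAEs related to participation | Patient is not in the Safety population (SAP 3.3.2) |

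Row 3 exposes a conflict. SAP 6.2 says that only treatment-emergent AEs are collected, while protocol 10.7.1 requires some earlier SAEs. Those SAEs have no assured place in the tables. At most they may appear in the listings that SAP Appendix 3 labels as covering all patients.

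The SAP is also divided on its safety denominator. Section 6 names the ITT population, in brackets, while Appendix 1 assigns the AE tables to the Safety population. Neither contains an irradiated, undosed patient.

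**Step 3: length of the gap.** For a dosed patient on schedule it is Days -2, -1 and 0, which is three days. For an undosed patient the routine window never opens.

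**Step 4: effect on a rate (illustration).** The documents give no frequency of blocked Dose 1, so the number of such patients, k, is an assumption. With n dosed patients, none with this outcome, the Safety population shows 0/n. Among all irradiated patients the figure is k/(n + k). Intervals are exact 95% (Clopper-Pearson).
- n = 21, as tabulated: 0/21 = 0% (0 to 16.1%).
- n = 21, k = 1: 1/22 = 4.5% (0.1 to 22.8%).
- n = 21, k = 2: 2/23 = 8.7% (1.1 to 28.0%).
- n = 21, k = 3: 3/24 = 12.5% (2.7 to 32.4%).
- n = 12, k = 1: 1/13 = 7.7%.

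The values 12 and 21 are evaluable counts, used here for the number dosed. Dosed patients who prove non-evaluable are replaced but stay in the Safety population. The true n may be larger and the share per omitted patient smaller.

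**The case against.** The strongest reply is that little is lost. Protocol 10.7.1 catches serious SBRT-related events from consent. By the protocol's own account the main radiation toxicities come late: pneumonitis after weeks to months (8.6.1), and radiation-induced liver disease at 2 weeks to 3 months (8.6.2). In a dosed patient these mostly fall inside the window and are recorded whatever their cause. Clinically significant worsening of an earlier problem also counts as a new AE (10.1). All of this stands. A reader might infer that SBRT toxicity as a whole goes unrecorded, or that the safety aim cannot be answered. The documents support neither. The aim's subject is the drugs given after radiation, and most of the relevant follow-up is covered.

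It can also be said that blocked Dose 1 may be rare. The toxicity check in 8.1 names hematologic, gastrointestinal and genitourinary toxicity, 4.1.13 ties these to chemotherapy, and the radiation goes to lung or liver. SAP 4.1 counts patients entered and treated, so an undosed patient could appear as the difference. This limits the likely size. It does not supply the reason for non-dosing, and it does not bring the patient into a safety table.

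A reader might go further and infer that the SAP baseline lets radiation effects pass as baseline and weakens the Hy's Law check. SAP 3.4 says: "The baseline is defined as the last assessment done before or on study day 1". The documents do not support that reading:
- Nothing applies SAP 3.4 to the criteria in protocol 8.7.1.
- The SAP plans no laboratory or change-from-baseline table.
- The Hy's Law discontinuation thresholds in 8.5.5 are multiples of ULN, with no baseline multiplier.
- Table 1 already requires liver tests before study entry.
- The 72-hour period before Day 1 in Table 2 reaches back to Day -2, so those tests need not follow the first fraction.

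**Conclusion.** The point holds in limited form. Recording is not required for non-serious AEs, or for SAEs not judged related to participation, that start between the first SBRT fraction and Dose 1. Pre-dose SAEs that are related to participation are recorded, but lie outside the treatment-emergent definition, and the SAP misdescribes the protocol on what is collected. Irradiated patients who cannot be dosed are called screen failures and fall outside the safety denominator.

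The size is modest: about three days per dosed patient, and an unknown number of undosed patients, each worth roughly 5 to 8 percentage points under the assumption of 12 to 21 dosed patients. The conclusion rests on reading study therapy as the drugs alone, which protocol 2.7.3, 4.2.24, 7.0 and 14.1 all support. It should be corrected because the omission of patients can depend on toxicity and the remedy is cheap. It does not affect the response-rate design.

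**What to change.** 1. In protocol 10.7.1 and 10.8, and in SAP 3.1.1 and 6.2, start AE and SAE recording and the treatment-emergent period at the first SBRT fraction. Keep recording SAEs related to participation from consent. Correct the SAP 6.2 statement so that it agrees with 10.7.1. State when the window closes for a patient who has no drug dose, since the present end is counted from the last dose.
2. In SAP 3.3.2, define the Safety population as patients who received at least one SBRT fraction or one drug dose, with undosed patients shown separately. Name this population consistently in SAP section 6 and Appendix 1.
3. In SAP 4.1 and Table 01.01, report these patients as 'irradiated, not dosed', with the reason, and not as screen failures. Align the reporting label in protocol 8.1. The rule on who may receive Dose 1 is unchanged.

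The cost is wording, plus about three more days of AE entry per dosed patient. Dosed patients need no extra visit, because Table 2 already has an AE assessment within 72 hours before Cycle 1 Day 1. Undosed patients need AE collection up to the chosen end date. The reported AE rate may be slightly higher. Sample size, error rates and power stay as they are.

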11.0 ASSESSMENT OF EFFECT

Response to study treatment in this patient population will follow standard RECIST criteria except in the documentation of progressive disease (PD). In this protocol, patients with progressive radiographic metastatic disease who are clinically asymptomatic and without other significant reason to discontinue therapy (i.e., toxicity, physician's judgement or patient's decision to stop therapy) may continue to receive study therapy per protocol until the next scheduled tumor assessment ([Table 2](#)) to confirm progression. If progression is confirmed the date of progression will be at the time of the initial scan indicating progression.

11.1 Definitions of measurable and non-measurable disease

11.1.1 *Measurable disease:*

Measurable lesions are defined as those that can be accurately measured in at least one dimension (longest diameter to be recorded) as ≥ 20 mm with conventional techniques (PET/CT, CT scan, or MRI) or as ≥ 10 mm with spiral CT scan with 5 mm cuts. All tumor measurements must be recorded in millimeters (or decimal fractions of centimeters). The same method (CT, MRI, or PET/CT) used at baseline should be used at all other tumor measurement time points.

11.1.2 *Non-measurable disease*

All other lesions, including small lesions (longest diameter < 20 mm with conventional techniques or < 10 mm using spiral CT scan with 5 mm cuts) are considered to be non-measurable disease.

11.1.3 *Target lesions*

Up to a maximum of five measurable lesions should be identified as target lesions and recorded and measured at baseline. Target lesions (maximum 2 lesions per organ) should be selected on the basis of their size (lesions with the longest diameter) and their suitability for accurate repeated measurements by CT scan or MRI. A sum of the longest diameter (LD) for all target lesions will be calculated and reported as the baseline sum LD. The baseline sum LD will be used as reference by which to characterize the objective tumor response.

11.1.4 *Non-target lesions*

All sites of disease which are not used as target lesions should be identified as non-target lesions. Location of individual lesions within the liver does not have to be specifically recorded. All sites of non-target lesions must be assessed along with the target lesions.

11.2 Response criteria

11.2.1 *Evaluation of target lesions*

- *Complete response (CR)*
Disappearance of all target lesions
- *Partial response (PR)*
At least a 30% decrease in the sum of the of LD of target lesions, taking as reference the baseline sum LD

- *Progressive disease (PD)*
At least a 20% increase in the sum of the LD of target lesions, taking as reference the smallest sum LD recorded since baseline or the appearance of one or more new lesions
- *Stable disease (SD)*
Neither sufficient shrinkage to qualify for PR nor sufficient increase to qualify for PD, taking as reference the smallest sum LD since baseline

11.2.2 *Evaluation of non-target lesions*

- *Complete response (CR)*: disappearance of all non-target lesions,
- *Incomplete response/stable disease (SD)*: persistence of one or more non-target lesion(s).
- *Progressive disease (PD)*: Appearance of one or more new lesions and/or unequivocal progression of existing non-target lesions.

11.2.3 *Evaluation of best overall response*

The best overall response is the best response recorded from the start of the treatment until disease progression/recurrence (taking as reference for progressive disease the smallest measurements recorded since the treatment started).

Refer to [Table 8](#) for a summary of the criteria that contribute to the determination of response.

Table 8. Determination of response

Target Lesions	Non-Target Lesions	New Lesions	Overall Response
CR	CR	No	CR
CR	Incomplete response/SD	No	PR
PR	Non-PD	No	PR
SD	Non-PD	No	SD
PD	Any	Yes or No	PD*
Any	PD	Yes or No	PD*
Any	Any	Yes	PD*

*Confirmation of PD in a patient with new lesion(s) or suspected tumor flare is required as outlines in [Sections 11.2.1](#) and [11.2.2](#).

11.3 **Symptomatic deterioration**

Patients with a global deterioration of health status requiring discontinuation of treatment without objective evidence of disease progression at that time should be reported as "symptomatic deterioration." This is also true for "symptomatic deterioration" after therapy is completed. Every effort should be made to document objective progression even after discontinuation of treatment.

